# Phase II Hypotheses:

**AIM 1 Hypotheses:** Children of fathers who receive F4C (n=180), relative to BIP (n=180), will: (1a) experience less family violence (FV), (1b) have more positive father-child interactions, and (1c) have lower FV-related mental health symptoms (PTSD, internalizing/externalizing) at post treatment and 6- and 12-month follow-ups. The effects of both treatments on father and coparent mental health outcomes will also be examined (1d exploratory). Hypotheses will be evaluated with the broad family of latent (growth) curve models (LGM), which estimate and compare trajectories of change for each case in the data. Group differences in changes will be tested in multiple group LGM models. Following analyses for our primary study hypotheses, we will examine whether child sex moderates child mental health outcomes between the F4C and BIP groups. Power. The planned sample size of 140 F4C and 140 BIP cases provides power of .91 to detect a small to moderate effect size (d = 0.12). The current study with 140 per group (even 126) per group assuming a conservative 30% attrition at follow-up) has sufficient power to determine small differences in changes between intervention groups on outcomes. LGM models for changes in latent rather than observed scores, for three or more waves of data, have the advantage of partialing out measurement error, and increasing the statistical power by at least 20%. See Statistical Design and Power Section for estimation method.

AIM 2 Hypotheses. Compared to BIP, more F4C fathers will show profiles of healthy change in therapeutic targets: (2a) masked coding of in-session RF/ ER (i.e., increased RF and adaptive ER, decreased maladaptive ER), and (2b) between-session self-reported RF/ ER (i.e., increased

RF and adaptive ER, decreased maladaptive ER). F4C change profiles will reveal critical junctures in treatment that precipitate therapeutic change, thereby serving to optimize timing and delivery of treatment components (2c, exploratory). Group-based trajectory modeling from the family of latent growth mixture modeling (GMM) will be used first to examine the number of different trajectory groups and their profiles (e.g., stable low or high adaptative ER, gradual increase or decrease in RF level, initial increase, then stable RF level, rapid decrease followed by gradual decrease of maladaptive ER, etc.) during the intervention period, as well as determine whether F4C vs. BIP treatment conditions influence trajectory group membership. Initially, trajectories of each in-session and between-session therapeutic change target will be modeled separately. Because data are expected to have unequal measurement intervals, we will use a new feature in Mplus 8.8 for analyzing such data (i.e., *tinterval and dynamical SEM*), and explore a new Stata 17 module for irregular time spacing measurements (i.e., xtusreg).143 Subsequent models will simultaneously examine various combinations of these six related targets to identify appropriate group membership for the fathers. This therapeutic change grouping will be modeled as the mediating variable in subsequent mediation analyses. **Power.** Determining power in group-based trajectory modeling with unequal time gaps is complex and not well explored. Given that some applications have used the classical, similar analytic method, mixture LGM (with equal time gaps), to extract three classes with a sample size as low as 45,144 the current target sample size of 360 (or 252 with attrition) will be adequate to identify trajectory groups and test further differences between F4C and BIP groups.

**AIM 3. Hypotheses.** Profiles of healthy change in RF and ER will mediate the treatment effect of F4C over BIP on: (3a) FV (3b) father-child interactions, and (3c) child mental health (PTSD, internalizing/externalizing) at post-treatment and at 6- and 12-month follow-ups. LGM mediation models will be used to evaluate the mediating effect of therapeutic change classes on the treatment impact on both the fathers' use of FV and children's outcomes. In particular, the baseline predictor will be father's randomly assigned intervention group: F4C vs. BIP, with father's therapeutic change in RF and ER trajectory groups from Aim 2 entered as a categorical mediator into a structural equation model framework to investigate the mechanisms of change in child outcomes at post-intervention and up to two subsequent follow-ups. **Power.** Power analyses for mediational LGM models with categorical mediators are rare. The specialized Mplus 8.8 SEM software however has been advancing the toolbox available for such complex models, and its recent capabilities promise to provide adequate statistical power with the proposed sample size.

4. **Participant Population:** Provide a detailed description of the types of participants who will be recruited into this study.

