# Aims for Phase II:

AIM 1. Compare F4C to a standard BIP in its efficacy to reduce FV by decreasing fathers' violent behavior, improve father-child interactions, and reduce child mental health symptoms. *Hypotheses.* Children of fathers who receive F4C (n=140), relative to BIP (n=140), will: (1a) experience less FV, (1b) have more positive father-child interactions, and (1c) have lower FV-related mental health symptoms (PTSD, internalizing/externalizing) at post treatment and 6- and 12-month follow-ups. The effects of both treatments on father and coparent mental health outcomes will also be examined (1d *exploratory*).

AIM 2. Identify and compare latent change profiles of therapeutic targets (RF, ER) in F4C and BIP fathers across the 18-week intervention. *Hypotheses*. Compared to BIP, more F4C fathers will show profiles of healthy change in therapeutic targets: (2a) masked coding of insession RF/ ER (i.e., increased RF and adaptive ER, decreased maladaptive ER), and (2b)

between-session self-reported RF/ ER (i.e., increased RF and adaptive ER, decreased maladaptive ER). F4C change profiles will reveal critical junctures in treatment that precipitate change, thereby serving to optimize timing/delivery of treatment components (2c, *exploratory*).

AIM 3. Examine the mediating role of therapeutic change targets (RF, ER) on child-related outcomes in F4C and BIP families. *Hypotheses*. Profiles of healthy change in RF and ER will mediate the treatment effect of F4C over BIP on: (3a) FV (3b) father-child interactions, and (3c) child mental health symptoms (PTSD, internalizing/externalizing) at post-treatment and at 6- and 12-month follow-ups.

2. **Background:** Describe the background information that led to the plan for this project. **Provide references** to support the expectation of obtaining useful scientific data.

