Child Mental Health. Symptom dimensions will be derived from father and mother reports on surveys with established reliability, validity, and developmental sensitivity. For data reduction purposes, continuous latent constructs will be identified via measurement models and secondorder factor models conducted in Mplus using standard fit criteria. If necessary, we will use other methods to reduce these data, e.g., latent constructs formed by principal components analysis. The TSCYC and TSCC includes 8 subscales assessing trauma symptoms and more common childhood symptoms and are used for children aged 3 to 17. For infants and toddlers, we will have parents complete the Brief Infant Toddler Social Emotional Assessment (ITSEA) Stratified Randomization. To increase the likelihood treatment groups are balanced on important variables (i.e., , residence with target child, protective order with coparent, substance use) participants will be assigned to treatment through stratified randomization. Following randomization, fathers will be assigned to either 18 sessions (once per week) of Fathers for Change or18 sessions of Duluth Batterer Intervention delivered in an individual format. We anticipate 140 participants in each treatment group. Research assistants managing the data [name] will be blind to treatment condition assignment during analysis. Participants will be recorded as receiving either "treatment 1", or "treatment 2". The research assistants and [name] will not be aware which treatment protocol "treatment 1" or "treatment 2" correspond to until analyses are complete.

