# Phase II:

The target sample is 280 father-coparent dyads and their 9 months to 11 year-old children recruited from CPS-involved families referred to the Parent and Family Development Program (PFDP) at Yale or the UCONN Health Center Outpatient Psychiatry Clinic. Participants will be randomized to either F4C (n = 140) or BIP (n = 140) following a baseline assessment. Half of F4C and BIP families will be treated at Yale and half at UConn Health. Yale will serve families in

Greater New Haven region, while UConn Health will serve families in the Greater Hartford region. The two sites are approximately a 45-minute drive apart.

5. **Describe** how access to the population will be gained in the study.

Fathers referred to the Parent and Family Development Program or UCONN Health Center by the CT Department of Children and Families (DCF) or the community due to IPV or child maltreatment risk will be provided information about the study and asked to complete an initial brief screening if they are interested in participation. He will be told that his screening questionnaire (which will include demographic matching information such as age, ethnicity, city of residence, income, employment history, SA history etc.) will be reviewed and he will be contacted to set up further assessment sessions if he is found eligible by the PI based on our study's requirements. This will provide the opportunity for contact with the mother to conduct phone screening with her related to IPV and her willingness for their shared child to participate. Female co-parent and intimate partner contact information will be provided on the referral from DCF or community referral source so that fathers are not providing this information, and this will limit the possibility of coercion.

6. **Participant classification:** Check off all classifications of participants that will be specifically recruited for enrollment in the research project. Will participants who may require additional safeguards or other considerations be enrolled in the study? If so, identify the population of participants requiring special safeguards and provide a justification for their involvement.

🛛 Healthy	□Fetal material, placenta, or dead fetus
Prisoners	□Economically disadvantaged persons
🗆 Employees	□Pregnant women and/or fetuses
□ Females of childbearing pote	ential
	
 
Healthy
 
Prisoners
 
Employees
 
Females of childbearing pote
 

Click or tap here to enter text.

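### Aim 1 tests arm differences in change without stating a common baseline mean or baseline adjustment, which leaves open an avoidable loss of precision in the main efficacy test

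*Combined protocol and SAP*

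**What the plan says.** The Aim 1 paragraph under Phase II Hypotheses names latent growth curve models as the analysis family and gives the between-arm test in one sentence: "Group differences in changes will be tested in multiple group LGM models". Aims for Phase II sets the outcomes to be compared "at post treatment and 6- and 12-month follow-ups".

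On design, the Phase II part of Participant Population states: "Participants will be randomized to either F4C (n = 140) or BIP (n = 140) following a baseline assessment". The randomisation text says "participants will be assigned to treatment through stratified randomization", while the Analytic Plan calls the procedure urn randomisation. Both place allocation after baseline.

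The supplied text does not say whether intercept means are free or equal across arms. It does not mention the baseline value as a covariate, or the slope regressed on the intercept. The Preliminary Analysis paragraph plans to explore group differences in the urn variables and demographics, but names no baseline adjustment for Aim 1. For the estimation method, the Aim 1 paragraph refers to a Statistical Design and Power Section that is not in the supplied text.

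**The concern.** A multiple-group growth model fitted with its own intercept mean in each arm estimates a baseline difference that randomisation has already set to zero in expectation. The chance difference at baseline then enters the contrast in change, as it does in a comparison of change scores. Holding the baseline mean equal, or adjusting for baseline, removes that noise.

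The cost of leaving it in is precision, and it falls on the main efficacy comparison. The plan expects to detect small differences and anticipates at least 70% completion, so information already collected at baseline is worth using. The choice also affects the result, and the visible text leaves it open until after data are seen.

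**Working it through.** **Inputs.** 140 fathers per arm, from "The planned sample size of 140 F4C and 140 BIP cases". The same paragraph also gives 180 per arm, and its 126 after 30% attrition is 180 × 0.7; 140 × 0.7 = 98. I use 140, and 98 after attrition. Waves are baseline, post-treatment, 6 and 12 months (assessment schedule, Table 1). With 18 weeks of treatment these fall at about 0, 4.2, 10.2 and 16.2 months. Assumed because not stated: two-sided alpha .05, SD 1, correlations of .3 to .8.

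**The plan's own figure.** Aim 1 states power .91 for d = 0.12 with 140 per arm. A two-sample comparison gives 0.12 × √(140/2) = 1.00 standard errors, so power is .17 two-sided (.26 one-sided). Power of .91 would need 1,514 per arm two-sided, or a baseline-to-follow-up correlation of about .95 on change scores. Values near .91 appeared only with inputs the text does not give, such as reading 0.12 as Cohen's f. The figure does not reproduce, but the point here does not depend on it.

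**Two waves.** Up to the common factor 2σ²/n:

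- separate baseline means (change score): 2(1 − r)
- common baseline mean or baseline adjustment: 1 − r²
- ratio: (1 − r²) / [2(1 − r)] = (1 + r)/2

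The detectable effect at 80% power with 98 per arm is 2.80 × √(2/98) = 0.400, times the SD of the contrast: √[2(1 − r)] for separate means, √(1 − r²) for a common mean.

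| r (assumed) | Variance ratio | Variance cut | Equivalent extra fathers (1/ratio − 1) | Detectable d, separate | Detectable d, common |
|---|---|---|---|---|---|
| .3 | .65 | 35% | 54% | 0.474 | 0.382 |
| .5 | .75 | 25% | 33% | 0.400 | 0.347 |
| .7 | .85 | 15% | 18% | 0.310 | 0.286 |

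**Four waves, linear slope.** Fixing the intercept difference at zero multiplies the variance of the slope difference by 1 − c², where c is the correlation between the estimated intercept and slope differences. Under compound symmetry, with complete data at the wave times above, mean time is 7.65 and the sum of squares about it is 150.0. Then c² = 0.390(1 − ρ) / [ρ + 0.640(1 − ρ)], using 7.65²/150.0 = 0.390 and 0.25 + 0.390 = 0.640. At ρ = .5, c² = 0.195/0.820 = 0.24, so the ratio is .76. At ρ = .3, .5, .7 and .8 the ratios are .64, .76, .87 and .92, that is cuts of about 36%, 24%, 13% and 8%.

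**Other structures.** With random slopes or autoregressive correlation, the ratio ran from .49 to .98, a cut of 51% to 2%.

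**Illustrative power.** Take 140 per arm, complete data, compound symmetry, and a slope difference worth 0.30 SD at the last visit. Power moves from .62 to .81 (ρ = .3), .77 to .87 (ρ = .5) and .93 to .96 (ρ = .7). For 0.12 SD at ρ = .5 it moves from .19 to .23, still far below .91.

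**The case against.** The strongest objection is that the defect is inferred from silence. A multiple-group growth model can carry free intercept means, equal intercept means, or a slope regressed on the intercept, and the plan names none of these. The estimation detail may sit in the section that is not in the supplied text. This stands. A reader might infer that the sponsor has chosen separate baseline means and so ignores the randomisation; the documents do not support that. Nor do they support reading the analysis as biased: under randomisation, free intercepts neither bias the contrast nor inflate type I error.

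A second objection is that (1 + r)/2 is a two-wave, observed-score formula, while the plan uses latent models over several waves. The four-wave compound-symmetry results are close to it, so the formula does not mislead about direction or rough size. But the range over other structures starts at 2%, and no correlation or variance is given. The percentages and detectable effects above are therefore illustrations and not this trial's known loss.

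A third is that the remedy needs care. If change is concentrated in treatment and then levels off, a straight line misfits, and constraining its model-implied intercept can distort the slope contrast. Freeing all post-baseline means would be a different model from a growth curve, with several visit contrasts per outcome. Coded father-child play has no 6-month wave in Table 1, so no 6-month contrast exists for it. These points stand and shape the fix.

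**Conclusion.** The point holds as a gap in specification with an efficiency cost. The Aim 1 test is a between-arm difference in change, allocation follows baseline, and the supplied text states neither a common baseline mean nor baseline adjustment. If arm intercepts are left free, the contrast is valid but less precise than it need be.

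The likely variance saving is about 15% to 35% in the two-wave calculation (r = .7 to .3) and about 8% to 36% in the four-wave compound-symmetry model (ρ = .8 to .3), with 2% to 51% over the other structures. All of this rests on assumed correlations, and the four-wave results also on complete data. The amendment is worth making because the gain is supported by the design and costs little. It should not be read as a repair of the sample-size justification: power of .91 at d = 0.12 remains unexplained with or without the constraint.

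**What to change.** In the SAP, for each Aim 1 model:

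- Place time zero at baseline and hold the baseline (intercept) mean equal across F4C and BIP, or adjust for the baseline value of the outcome.
- Prespecify a time shape that lets change during treatment differ from change during follow-up, so that the constraint falls on the actual baseline mean and not on the intercept of a misfitting line.
- Estimate the arm difference from that model at the visits where the outcome is collected: post-treatment, 6 and 12 months in general, and post-treatment and 12 months only for coded father-child play.

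The cost is some model specification and SAP wording. No new data, visits or participants are needed, and under randomisation the equal-mean constraint carries no validity cost provided the time shape is adequate. If the unsupplied statistical section already specifies one of these options, bringing that sentence into the Aim 1 paragraph would settle how baseline is handled; the time shape and visit contrasts should be stated there as well.

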# Phase II:

Two hundred eighty fathers, the female *coparent of their youngest child*, and their youngest biological child aged 9 months to 12 years will participate for a total of up to 840 participants in this Phase 2 randomized controlled efficacy trial.

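### Phase II power after attrition uses 126 per arm, but a 30% loss from 140 leaves 98; the 126 belongs to a 180-per-arm design that is not the planned one

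*Combined protocol and SAP*

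**What the plan says.** The planned Phase II size is 140 fathers per arm, 280 in all. Section IV.1 (Aims for Phase II) says "Children of fathers who receive F4C (n=140), relative to BIP (n=140"), and the Research Plan in Section IV.3 opens with "Two hundred eighty fathers, the female" coparents and target children. The Stratified Randomization paragraph, Section IV.4 and the all-sites line of Section V.3 agree. Section V.4 applies at least 70% completion to 280 families and expects 196 complete cases.

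The Phase II Hypotheses text in the Analytic Plan differs:

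- The Aim 1 hypothesis reads "Children of fathers who receive F4C (n=180), relative to BIP (n=180").
- The Aim 1 power statement returns to the planned size: "140 F4C and 140 BIP cases provides power of .91 to detect a small to moderate effect size (d = 0.12").
- The next sentence gives the sample before and after loss as "140 per group (even 126) per group assuming a conservative 30% attrition at follow-up". From this it concludes that the trial "has sufficient power to determine small differences in changes between intervention groups on outcomes".
- The Aim 2 power statement says "the current target sample size of 360 (or 252 with attrition) will be adequate" for identifying trajectory groups.

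For the method the reader is told "See Statistical Design and Power Section for estimation method". No section of that name is in the supplied document.

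For Phase I, Section V.4 states 80% power for d = 0.45 at 18 weeks with 63 people, from 75 enrolled in three arms of 25.

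**The concern.** The 126 is the only after-attrition sample size offered in support of Aim 1, the Phase II efficacy aim, and it does not follow from the 140 and the 30% in the same sentence. It also conflicts with the completer count in Section V.4. A reader who accepts it will believe that power survives attrition with a wider margin than the planned sample gives.

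The second part concerns the powers themselves. A standardized difference of 0.12 is very small for 140 per arm, and 0.45 is modest for 63 fathers over three arms. Neither stated power follows from an ordinary two-group comparison. With no alpha, sidedness, effect metric or correlation stated, a reader cannot tell what effect either phase is sized to detect.

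**Working it through.** **1. Sample sizes (no assumption needed)**

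Inputs: 140 per arm, 280 in all, and 30% loss.

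- 140 × 0.70 = 98 per arm; 280 × 0.70 = 196, which reproduces Section V.4.
- 126 / 140 = 0.90, so 126 would be a 10% loss.
- 180 × 0.70 = 126 and 360 × 0.70 = 252. The figures 180, 126, 360 and 252 therefore form one exact set for 180 per arm.
- Excess completers cited: 126 − 98 = 28 per arm.
- Sites: Section V.3 targets 180 fathers at Yale, which leaves 280 − 180 = 100 for UConn Health. Section IV.4 splits families half and half, 280 / 2 = 140 per site. This 180 is a site target, not an arm size, but it needs reconciling too.

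**2. What the wrong number does to power**

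Accept the protocol's .91 at 140 per arm and assume a two-sided .05 test with one degree of freedom. The noncentrality is then 1.960 + 1.341 = 3.301, and it scales with the square root of n.

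| n per arm | noncentrality | power |
|---|---|---|
| 140 | 3.301 | .91 |
| 126 | 3.301 × √(126/140) = 3.131 | .88 |
| 98 | 3.301 × √(98/140) = 2.762 | .79 |

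At equal power, the detectable effect at 98 is √(140/98) = 1.195 times that at 140, and √(126/98) = 1.134 times that at 126.

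The planned growth models can use dropouts' earlier visits. To allow for this, take a generalized least squares slope test with compound symmetry and waves at 0, 4.14, 10.14 and 16.14 months (18 weeks of treatment, then 6 and 12 months). Set the effect so that 140 complete per arm gives .91, with 42 lost per arm.

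| pattern of loss | r = .3 | .5 | .7 | .8 |
|---|---|---|---|---|
| 14 lost after each of the first three waves | .833 | .825 | .819 | .816 |
| all 42 lost after baseline | .824 | .813 | .803 | .798 |
| all 42 lost before the last wave | .848 | .845 | .843 | .843 |
| father-child play: three waves, 21 lost after each of the first two | .818 | .810 | .803 | .800 |

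Play has three waves because Table 1 schedules it at 12 months but not at 6. As a further check, group-by-time F tests set to .91 at N = 280 give .875 to .879 at 252 and .77 to .79 at 196 (two to four waves).

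**3. Can the stated powers be reproduced?**

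As a two-sample t test at one time point, two-sided .05:

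- Phase II, d = 0.12: .17 at 140 per arm and .13 at 98, against the stated .91.
- Phase I, d = 0.45: .30 (21 v 21) and .38 (21 v 42), or .34 (25 v 25) and .44 (25 v 50) with all 75 fathers, against the stated 80%.

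As a group-by-time F test with noncentrality λ = f²·N·m/(1 − ρ), df1 = (k − 1)(m − 1) and df2 = (N − k)(m − 1), for k groups and m waves:

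- Phase II, N = 280, f = d/2 = .06: .91 at ρ = .73 over four waves, or at ρ = .82 over two. At ρ = .5 it is .66, .58 and .52 for four, three and two waves.
- Phase II with 0.12 read as f: .91 at ρ = .27 over two waves.
- Phase I, N = 63, three groups, two waves, f = .225: .75 at ρ = .3, .82 at ρ = .4, and 80% at about ρ = .37.

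The stated values are therefore reachable under some choices, but the document states none of those choices. The Phase I attrition step is sound: 63 / (1 − 0.16) = 75.

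**The case against.** The arithmetic cannot be defended, so the case on the other side is about consequence.

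- **Partial follow-up.** The analysis uses latent growth models, and the protocol intends to retain dropouts for intention-to-treat analysis, so .79 for completers is the least favourable figure. This stands: with partial data kept, power is about .80 to .85 if .91 is right. Every one of those values is still below the .88 that 126 implies.
- **The .91 is itself unverified.** It might be left over from the 180-per-arm design. This also stands, so .79 and .88 are conditional illustrations and not the trial's power. The protocol gives no numerical power after attrition.
- **The 20% larger effect is mostly ordinary attrition.** Correct: 20% compares 98 with 140. The part due to citing 126 in place of 98 is about 13%, on completers.
- **The claimed gain of at least 20% in power from latent scores.** The protocol does not say whether .91 includes it. As a relative gain it cannot sit on top of .91, since .91 × 1.2 = 1.09. It does not alter the count of 98.
- **The power inputs may be in the section that was not supplied.** Possible. For that reason the second part is put as a reporting gap.
- **The plan already holds the right number.** Section V.4 does give 196. But the two sections then contradict each other, and the power claim cites the wrong one.

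**Conclusion.** The concern holds. It is certain, without any assumption, that 30% attrition from 140 leaves 98 per arm and not 126, and that 180, 126, 360 and 252 describe a 180-per-arm design in conflict with the planned 140. The statement that power is sufficient after attrition should not stand on 126.

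The size of the consequence depends on accepting .91 at 140 and a two-sided .05 test. On that footing power is about .79 for completers, and about .80 to .85 with partial follow-up over correlations of .3 to .8, where 126 would give .88. Power may still be judged acceptable, but that judgement has to be made from 98.

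That the stated powers in both phases cannot be reproduced is a lesser point: missing inputs, with no miscalculation shown. Aim 2's figures need the same correction, but its argument, which cites trajectory work with as few as 45 cases, is unaffected.

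**What to change.** - In the Aim 1 text of the Phase II Hypotheses, change 180 to 140 for both arms and 126 to 98.
- In the Aim 2 power text, change 360 and 252 to 280 and 196.
- Reconcile the Yale target of 180 fathers in Section V.3 with the half-and-half site split in Section IV.4.
- For both phases, state alpha, sidedness, the effect metric and the assumed correlations in this document.
- Recompute Phase II power for the planned growth model at 140 and 98 per arm, with father-child play at three waves.
- Recompute Phase I power for the mixed model at 25 and 21 per arm for each named contrast: F4C against each BIP arm, or against BIP pooled if that is meant.
- Restate the power or the detectable effect, and keep the claim of sufficient power after attrition only if the new figure supports it.

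The cost is protocol wording and one re-run of the power calculations. Enrolment, visits and the analysis model do not change. The restated after-attrition power may be less favourable.
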